### ***Innovation:***

#### **Percutaneous Electrical Nerve Field Stimulation (PENFS)**

An FDA-approved auricular device, IB-Stim, that utilizes the concept of PENFS to alleviate pain has recently been developed by Innovative Health Solutions (Versailles, IN, USA). This device uses discontinuous frequencies of stimulation to target central pain pathways through branches of cranial nerves V, VII, IX, and X that innervate the external ear and project to certain brainstem nuclei, including the nucleus tractus solitarius. As previously mentioned, Kovacic et al recently conducted a double-blind, randomized, sham-controlled trial evaluating PENFS in 115 children with abdominal-pain-related functional GI disorders. Children in the PENFS group had a greater reduction in their worst abdominal pain and overall composite pain scores compared with sham after 3 weeks of treatment, and these effects were sustained over an extended follow-up period of 8-12 weeks.

Children in the PENFS group also had a reduction in their worst pain of  $\geq 30\%$  from baseline to 3 weeks of treatment compared with children in the sham group. Additionally, children in the PENFS group had greater scores on the Symptom Response Scale (median score of 3) compared to children in the sham group (median score of 1) at the end of 3 weeks; however, these effects were no longer significant at extended follow-up. Patients who received PENFS also showed significant improvement in functional disability at extended follow-up compared to the sham group. Side effects from the therapy were minimal (6 patients reported ear discomfort, 3 reported an adhesive allergy, and 1 reported syncope from needle phobia) and no serious adverse events were observed. This is consistent with a previously published retrospective cohort study of over 1,200 patients that reported minimal to no side effects with PENFS used for other indications. In June 2019, the FDA approved the use of Innovative Health Solutions' device, IB-Stim, to treat functional abdominal pain associated with IBS in adolescent patients between the ages of 11 and 18 years old. Again, there are currently no trials of PENFS in adult IBS patients.

#### **Smart Watch Technology**

In collaboration with a UCLA research group led by [name] (IRB IRB#16-000166) participants will have the option to be given a SmartWatch system. This system includes ambient location and activity sensors, wireless data transmission, specialized software application, and analytic engine for functional and performance measurement. This platform allows for the detection and classification of patient motion and position with an accuracy of over 85%. In this study, we want to be able to monitor subject activity and abdominal pain in real time. Data will also be collected to measure HRV. With collected of HRV data in a standard manner with each in-person visit, we will be able to validate SmartWatch measurements of HRV.

**Research Approach:****1. Trial Design and Participants**

We will perform a prospective, double-blind, randomized, sham-controlled pilot study evaluating the efficacy of PENFS for the treatment of adult patients with IBS. Patients will be recruited from the outpatient GI clinics within the Vatche and Tamar Manoukian Division of Digestive Diseases at UCLA, as well as through community advertisements for physiologic or treatment related clinical trials and research studies by the UCLA G. Oppenheimer Center for Neurobiology of Stress and Resilience. New IBS patients or returning IBS patients who have continued abdominal pain even in the presence of medical therapy will be identified for participation in the study. The study will be approved by the institutional review board at UCLA.

An informed consent form will also be approved by the UCLA institutional review board and will be signed by all eligible patients prior to participation in the study (consent will be conducted via telephone and patients will bring signed consent form to the first visit). Patients will be compensated \$25 each time they participate in device placement and/or questionnaires (total compensation \$175). Parking will be provided at the Ronald Reagan UCLA Medical Center for each visit. Driving compensation will also be provided for eligible participants. \$50 will be compensated to participants if they live greater than a 10 mile distance from UCLA and \$75 will be compensated to participants if they live greater than a 25 mile distance. Driving compensation will be provided through either a gift card or through addition to the subject's stipend, via the participant's preference.

Patients will be allowed to continue any medication regimens that they are on prior to enrollment in the study as long as the doses are stable, meaning there can be no changes to medication doses that have been shown to relieve abdominal pain within 60 days of enrollment in the trial and to all other medications within 30 days. The use of all medications will be carefully monitored each week to ensure that patients maintain consistent medication doses during the entire study. The initiation of new medications or non-pharmacologic treatment for abdominal pain or other IBS symptoms will not be permitted during the trial period.

Allowed concomitant therapy will include:

- Fiber supplements (i.e. psyllium)
- Polyethylene glycol (PEG)
- Lactulose
- Milk of magnesium
- Magnesium hydroxide
- Bisacodyl
- Sennosides
- Lubiprostone
- Linaclotide
- Plecanatide
- Loperamide
- Eluxadoline
- Cholestyramine, colestipol, colesevelam
- Alosetron
- Rifaximin
- Dicyclomine

- Hyoscyamine
- Peppermint oil (i.e. Ibgard)
- Tricyclic antidepressants (i.e. amitriptyline, nortriptyline, imipramine, desipramine)
- Selective serotonin reuptake inhibitors (i.e. citalopram, paroxetine, fluoxetine)
- Selective norepinephrine reuptake inhibitors (i.e. duloxetine)
- Probiotics

During the consent call, participants will be introduced to the option of the SmartWatch system. The system includes a watch and sensors. The watch interacts with the passive Bluetooth sensors to track the wearers activity. If participants elect to use the SmartWatch system, they will receive a daily question on the watch related to abdominal pain. This will allow researchers to track abdominal pain in real time. If participants do not elect to use the SmartWatch, they will complete this same daily abdominal pain question via an online questionnaire.

**2. *Mandatory inclusion criteria:***

- Adults, aged 18-60 years, who are able to provide written, informed consent
- Patients must meet Rome IV criteria for IBS, confirmed by a gastroenterologist who specializes in functional GI disorders. Any of the IBS bowel habit subtypes (diarrhea, constipation, mixed bowel habits, unclassified) will be allowed.
- Average daily worst abdominal pain score between 4 and 8 (on a 0-10-point rating scale).
- Minimum of 2 days of abdominal pain/week prior to starting trial.
- At least moderate IBS symptom severity with an IBS-SSS  $\geq 175$  (total score range 0-500).

**3. *Preferred, but not mandatory, inclusion criteria:***

- Ability to wear SmartWatch on the upper extremity (left or right wrist)
- Willingness to have SmartWatch system sensors installed in home (30-60 minute process)

**4. *Mandatory exclusion criteria:***

- Patients under the age of 18 years or over the age of 60 years
- Patients who cannot provide informed consent or do not speak English
- Comorbid, organic medical conditions associated with abdominal pain, including:
  - Inflammatory bowel disease, chronic liver disease, peptic ulcer disease, celiac disease, diverticulitis, appendicitis, colorectal cancer, endometriosis, pregnancy, other intestinal or extra-intestinal malignancies
  - Patients with overlapping functional GI disorders (i.e. functional dyspepsia) will not be excluded as long as IBS is their predominant disorder
- History of surgery involving CN V, VII, IX, or X. History of abdominal surgeries other than appendectomy or cholecystectomy at least 6 months before entry into trial.
- Patients on chronic opioids, benzodiazepines, or with illicit substance use
- Patients with underlying neurologic conditions, including history of:
  - Seizures, CVA, uncontrolled migraines, traumatic brain injury, multiple sclerosis
- Patients with underlying psychiatric conditions
- Patients with dermatologic conditions affecting the ear, face, or neck region (i.e. psoriasis), or with cuts or abrasions to the external ear that would interfere with needle placement
- Patients with hemophilia or other bleeding disorders

[figure not shown]
- j. Patients with any implanted electrical device
- k. Patients who are pregnant or breastfeeding
- l. Movement disorder

##### **5. Preferred, but not mandatory, exclusion criteria:**

- a. Unwillingness to wear the SmartWatch on upper extremity (left or right wrist) or have SmartWatch sensors installed in their home.

##### **6. Technology**

The IB-Stim/PENFS device consists of a battery activated generator and wire harness that connects to the generator. Four leads are also attached to the generator, each with a sterile 2 mm, titanium needle. Prior to device placement, the patient's ear is cleaned with alcohol wipes and the ear is trans-illuminated to identify neurovascular bundles that are avoided during needle placement. The generator is attached with adhesive to the skin behind the patient's ear, just above the mastoid process. Each of the 2 mm needles are inserted into the dorsal and ventral aspects of the ear, within 1-1.5 mm of the visualized vascular branches to create a field effect. The PENFS device settings are standardized and deliver 3.2 volts with alternating frequencies (1 ms pulses of 1 Hz and 10 Hz) every 2 s. This stimulation targets central pain pathways through branches of cranial nerves V, VII, IX, and X, which innervate the external ear. The PENFS device generator has a battery life of 5 days and delivers stimulations in 2-hour cycles. Patients remove the device at home on day 6 of treatment. Original protocol from Kovacic et al.

**Figures taken from Roberts et al (2016)**

SmartWatch Software:

Each SmartWatch contains a proprietary web-based application that is able to record, analyze and transmit activity data.

Environmental Sensors/Beacons

Sensors are 2.4 GHz radio using Bluetooth 4.0 Smart, also known as BLE or Bluetooth low energy beacons. These beacons are similar to small lighthouses that use only radio waves to communicate with any smart device in the range of 40-50 meters. Smart devices, such as smartwatches, can receive the beacons' signals and estimate the distance by measuring the received signal strength.

## 7. Study Protocol

### ***Randomization and Masking:***

Patients who meet study eligibility criteria will be randomly assigned (1:1) in blocks of two and four, using a code generated by a randomization program to 4 weeks of stimulation with an active or inactive (sham) PENFS device. Allocation will be concealed, and all physicians, statisticians, participants, and research coordinators will be unaware of device codes. One research coordinator who has no patient contact (CL) will be unblinded and handle allocation and storage of devices.

The sham devices will be identical to the active devices but will not administer electrical charges. Per manufacturer design and patient anecdotal experience from previous studies, both active stimulation and sham are below detectable sensation threshold. Per report from previous studies, some patients may experience a sensation around the ear after percutaneous needle placement; however, this sensation can occur with equal likelihood in the active or sham device. All subjects will be asked if they believe they were randomized to the active PENFS therapy arm or the sham therapy arm at the end of 4 weeks of treatment, and these results will be analyzed.

### ***Assessments and Questionnaires:***

Administration of questionnaires throughout the study is shown in Table 1 and Figure 2.

Patients will provide telephone consent for enrollment into the study. During the this phone call, the investigator will obtain the participant's medical and medication history to check eligibility. After enrollment, patients will complete an online daily questionnaire to assess daily stool consistency (7-point Bristol Stool Form Scale [BSFS]) and a daily question pertaining to daily worst abdominal pain (measured using an 11-point scale) that will be delivered by the smart watch, for one week prior to device placement. If patients do not elect to use the SmartWatch, then they will complete the daily question pertaining to daily worst abdominal pain via an online questionnaire. The questionnaires will provide a baseline for daily worst abdominal pain and stool consistency. In order to be enrolled into the study, patients must have an average daily worst abdominal pain score between 4 and 8, have a minimum of 2 days per week of abdominal pain, and have completed at least 4 out of 7 of the daily worst abdominal pain questionnaires.

If enrollment criteria are met, patients will then present to the UCLA G. Oppenheimer Center for Neurobiology of Stress and Resilience one week after enrollment for their first visit, where they will get a physical examination, complete additional questionnaires, undergo a measurement of HRV, and have the initial PENFS device placed by a trained health care professional (LC, AL, EL). After initial device placement, patients will be instructed to return to UCLA every 7 days (leeway of +/- 2 days in each direction will be allowed) for a total of 4 visits for device replacement and completion of additional questionnaires. Four different devices will be placed in total (at the start of weeks 1, 2, 3, and 4).

Although the IB-Stim device is currently FDA approved for use for 3 consecutive weeks, children in the original study by Kovacic et al actually received 4 consecutive weeks of device treatment. The authors chose to analyze the data after 3 consecutive weeks as children did not return to the clinic after the 4th week of treatment. However, we will analyze IBS symptom severity, abdominal pain, bloating, and bowel habits after the completion of the 4th week of treatment. Again, actual stimulation time is 5 days per week with 2

days off during each of the 4 consecutive weeks. The device is not waterproof and should be protected from water exposure. Patients will be instructed to either place a washrag in a small bowl and hold it over the ear while showering or will be provided with dry shampoo.

#### **Bowel Habit Classification:**

Bowel habits, defined by IBS-C, IBS-D, IBS-mixed type (IBS-M), and IBS-unclassified (IBS-U) will be assessed at baseline using the Rome-IV questionnaire.

#### **Bowel Symptom Questionnaire (BSQ):**

The BSQ evaluates general abdominal symptoms, GI tract specific symptoms, and bowel habits. It measures the severity of abdominal pain over the preceding week using a numerical scale ranging from 0-20, with 0 representing no pain and 20 representing the most intense pain imaginable. This questionnaire will also evaluate bloating and the severity of overall IBS symptoms over the previous week, again using numerical rating scales from 0-20, with 0 corresponding to “no sensation/symptoms” respectively, and 20 referring to the “most intense sensation/symptoms imaginable”. The BSQ will be measured at visit 1 for each patient in the trial.

#### **UCLA CNSR Participant Demographics:**

The UCLA CNSR Participant Demographics questionnaire will collect demographic information from study participants. The CNSR Participant Demographic questionnaire will be completed at visit 1 for each participant.

#### **Primary Endpoint:**

#### **IBS Severity Scoring System (IBS-SSS)**

The primary aim of this study is to compare the efficacy of PENFS versus sham therapy on the improvement of symptom severity after 4 weeks of treatment in adult patients with IBS, using the IBS-SSS. The primary endpoint is the mean change in IBS-SSS at the end of week 4 compared to baseline. This questionnaire is a validated measure of IBS symptom severity and has been shown to be responsive to treatment in different studies. It assesses severity of abdominal pain, frequency of abdominal pain, severity of abdominal distention, dissatisfaction with bowel habits, and interference of IBS with daily life over a 10-day period. Each of the five categories will receive a score from 0-100, and the total IBS-SSS is calculated by taking the sum of these categories (total score range 0-500). Patients will complete the IBS-SSS at week 1, after week 4 of treatment, and at extended follow-up (after 8 weeks). The IBS-SSS will be completed in person at visit 1 and via an online survey at the end of week 4 and during the extended follow-up period at week 8. The online survey will be emailed to the patients the day it is to be completed, and a reminder email will be sent if the survey is not submitted. Improvement in symptom severity will be assessed using a mean change in IBS-SSS score from baseline to 4 weeks after treatment and from baseline to 8 weeks after treatment.

#### **Secondary Endpoints:**

#### **IBS-SSS Responder Rate**

In addition, one secondary endpoint of this study will be to assess the proportion of clinical responders, using the IBS-SSS. Clinical responders at the end of 4 weeks and at extended follow-up will be defined as those that have  $\geq 50$ -point decrease on the IBS-SSS score from baseline. This is based upon a study by

Francis et al that demonstrated that a reduction in 50-points correlated with clinically meaningful improvement. Another secondary endpoint is the mean change in IBS-SSS at the end of the extended follow up period at week 8 compared to baseline.

### **Daily Worst Abdominal Pain**

Other secondary endpoints of this study is the change in weekly average of the daily worse abdominal pain after 4 weeks of treatment compared to baseline and the proportion of patients with a ≥30% reduction from baseline in the weekly average of the daily worst abdominal pain scores after 4 weeks of treatment. A ≥30% reduction in worst abdominal pain score is a recommended primary endpoint by the Food and Drug Administration for IBS treatment trials and has been used in multiple clinical trials. As previously mentioned, if participants elect to use the SmartWatch system, the watch will deliver one question assessing daily worst abdominal pain to each participant's watch for one week prior to device placement to obtain a baseline. This daily worst abdominal pain will be measured using an 11-point numeric rating scale. The smart watch will then deliver the same question assessing daily worst abdominal pain for the duration of the study. If the participant elects to not use the SmartWatch system, then this same question pertaining to daily worst abdominal pain will be completed via an online questionnaire, for the duration of the study.

### **Patient Reported Outcomes Measurement Information System (PROMIS)**

The PROMIS Gastrointestinal Belly Pain Scale is a validated questionnaire that assesses the severity of abdominal pain in adult patients over the previous 7 days. This scale incorporates aspects of abdominal pain intensity, discomfort, location, frequency, predictability, and extent to which the pain is bothersome.

The PROMIS Gastrointestinal Gas and Bloating Scale assesses the frequency and intensity/severity of bloating, the appearance of abdominal swelling, flatulence, and abdominal gurgling/rumbling, and the degree to which bloating is bothersome or interferes with daily activities over the past 7 days.

The PROMIS Gastrointestinal Constipation Scale will be used to assess the frequency and intensity of incomplete evacuation, rectal pain, straining, and hard stools. This scale will measure the extent to which constipation is bothersome or interferes with daily activities over the past 7 days. The PROMIS Gastrointestinal Diarrhea Scale will be utilized to evaluate the frequency and severity of loose to watery stools and urgency during the previous 7 days.

Each of the above PROMIS GI scales will be scored using percentile scores that are based on the general population. In order to accurately obtain percentile scores, the scale of each PROMIS question will be converted from 1-5 to 0-4. PROMIS questionnaires assessing bowel habits and the severity of abdominal pain and bloating will be assessed at baseline (visit 1), after each week of treatment (after weeks 1-4), and at extended follow-up. The questionnaires will be completed in person at baseline (visit 1) and after weeks 1-3 (visits 2-4), and via online surveys after 4 weeks and 8 weeks. Response will be assessed by the change in composite abdominal pain scores, bloating scores, constipation scores, and diarrhea scores from baseline to 4 weeks after treatment and from baseline to 8 weeks (extended follow up) after treatment.

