***Secondary Aims:***

To compare the efficacy of PENFS therapy versus sham therapy on:

1. the change in mean IBS-SSS at week 8 compared to baseline.
2. the proportion of adult patients with IBS who experience at least a 50-point reduction on the IBS-SSS after 4 weeks of treatment and at the extended follow up period at week 8. These patients are considered clinical responders.
3. the proportion of adult patients with IBS who experience an improvement of  $\geq 30\%$  from baseline in weekly average of the daily worst abdominal pain scores after 4 weeks of treatment. These participants are considered a responder.
4. the change in mean weekly average of the daily worst abdominal pain scores after 4 weeks compared to baseline in adult patients with IBS.
5. the change in average weekly abdominal pain symptoms after 4 weeks of treatment and at extended follow-up (8 weeks) compared to baseline, assessed through the PROMIS Gastrointestinal Belly Pain Scale.
6. the change in average daily stool consistency after 4 weeks of treatment compared to baseline, assessed using the Bristol Stool Form Scale (BSFS).
7. the change in average weekly bowel habits after 4 weeks of treatment and at extended follow-up (8 weeks) compared to baseline, assessed through the PROMIS Gastrointestinal Constipation Scale and Gastrointestinal Diarrhea Scale.
8. the change in average weekly bloating symptoms after 4 weeks of treatment and at extended follow-up (8 weeks) compared to baseline, assessed through the PROMIS Gastrointestinal Gas and Bloating Scale.
9. the change in IBS-QOL in adult patients with IBS after 4 weeks of treatment and at extended follow-up (8 weeks) compared to baseline.
10. the change in resting cardio-autonomic tone, i.e. HRV, over 4 weeks of treatment compared to baseline.
11. the safety and tolerability of PENFS therapy versus sham therapy in adult patients with IBS.

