### Statistical Analysis

Fisher tests will be used to evaluate for differences in categorical variables and a 2-tailed t-test and Mann-Whitney-U (MWU) test will be used for assessing differences between normally distributed continuous data and non-normally distributed continuous data, respectively. The data will be analyzed using R statistical analysis software.

The change in IBS-SSS score from baseline will be computed using a generalized linear mixed effect model. We will include treatment, time, and treatment x time as covariates. Tukey's honestly significant difference will be used for multiple comparisons. Data will be analyzed based on a modified intention-to-treat approach. Specifically, patients with less than one full week of data will be excluded from the study.

For all the secondary Aims, a simple 2-sample analysis (T-, MWU or Fisher's) test for changes in outcomes will be performed.

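### PROMIS change is analysed in general-population percentiles, a non-linear scale that compresses benefit in severe patients; this costs precision and interpretability on secondary aims 5, 7 and 8

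*Combined protocol and SAP*

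**What the plan says.** The PROMIS subsection under Secondary Endpoints covers four scales: belly pain, gas and bloating, constipation, and diarrhea. On scoring it says "Each of the above PROMIS GI scales will be scored using percentile scores that are based on the general population", and it gives the item recoding as a step towards that: "In order to accurately obtain percentile scores, the scale of each PROMIS question will be converted from 1-5 to 0-4". No other PROMIS score is named. The analysis variable follows in the same subsection: "Response will be assessed by the change in composite abdominal pain scores, bloating scores, constipation scores, and diarrhea scores from baseline to 4 weeks", and again to week 8.

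Under Secondary Aims these scales serve aims 5 (belly pain), 7 (constipation and diarrhea) and 8 (bloating). Statistical Analysis prescribes for every secondary aim "a simple 2-sample analysis (T-, MWU or Fisher's) test for changes in outcomes will be performed", with no adjustment for baseline or subtype.

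The inclusion criteria require IBS-SSS of at least 175 and average daily worst pain of 4 to 8. On subtype they say: "Any of the IBS bowel habit subtypes (diarrhea, constipation, mixed bowel habits, unclassified) will be allowed". Nothing restricts the constipation or diarrhea scale to patients who have that symptom.

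**The concern.** A percentile is a rank in the reference population. It moves quickly near the median, where people are dense, and slowly in the tails. A trial that selects patients with at least moderate symptoms works mainly on the slow part. Two patients with the same real improvement can then contribute very different percentile changes, and the smaller one comes from the sicker patient. The mean difference between arms becomes a weighted effect whose weights depend on baseline severity. That makes it hard to interpret, hard to compare with other trials, and awkward for planning a larger study, which is a main use of a pilot.

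Precision is also at stake. If the treatment signal shrinks faster than the random variation, power falls for no compensating gain, in a trial aiming for only 35 per arm.

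**Working it through.** **No plan figure to reproduce.** The only sample-size statement (22 per arm, 95% power) concerns a 30% reduction in worst daily pain. The documents state no power, baseline value, SD or effect for any PROMIS scale. Everything below except the 35 per arm and the two-tailed test is therefore assumed.

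**Step 1: compression.** Let z be severity in SDs above the general-population mean, and take the reference population as normal. The percentile is 100·Φ(z), so an improvement of 0.5 SD from z is worth 100·[Φ(z) − Φ(z − 0.5)].

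| Start | Calculation | Percentile points |
|---|---|---|
| z = 0 | 50.0 − 30.9 | 19.1 |
| z = 1 | 84.1 − 69.1 | 15.0 |
| z = 1.5 | 93.3 − 84.1 | 9.2 |
| z = 2 | 97.7 − 93.3 | 4.4 |

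From z = 1 to z = 2 the same benefit shrinks by a factor of 15.0/4.4 = 3.4.

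**Step 2: noise.** With baseline SD 0.7 and a pure-noise change of SD 0.7, the SD of the percentile change is 20.9 when the baseline mean is z = 0, 17.3 at z = 1, 13.7 at z = 1.5 and 10.0 at z = 2. From z = 1 to z = 2 the noise shrinks by 17.3/10.0 = 1.7, less than the signal. (Step 1 is for a patient starting exactly at z; averaged over a spread of baselines the contrast is milder.)

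**Step 3: power at 35 per arm, two-sided 0.05 (alpha is not stated in the plan).**

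*Set A*: baseline SD 0.7, SD of change 0.7, sham improvement 0.3. The active-minus-sham effect is 0.5 if all patients are symptomatic. In the mixed case it is 0.8 in the symptomatic half, and the other half sits at z = −0.5 with no change. 6,000 simulated trials; cells show linear score / percentile.

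| Symptomatic mean | All symptomatic, t | All symptomatic, Mann-Whitney | Half symptomatic, t | Half symptomatic, Mann-Whitney |
|---|---|---|---|---|
| z = 1 | 84% / 78% | 82% / 77% | 54% / 48% | 50% / 44% |
| z = 1.5 | 83% / 71% | 82% / 75% | 53% / 41% | 50% / 39% |
| z = 2 | 83% / 61% | 81% / 71% | 54% / 32% | 50% / 35% |

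*Set B*: baseline SD 0.5, SD of change 0.6, no sham improvement, half the patients symptomatic with an effect of 0.8, the rest at z = 0 with none. The t-test has about 70% power on the linear score. On percentiles it has 60% at z = 1, 47% at z = 1.5 and 30% at z = 2. Mann-Whitney at z = 2: 66% against 39%.

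*All symptomatic, baseline SD 0.5*, with an effect giving about 87% power on the linear score: about 84% on percentiles at z = 1 and 67% at z = 2.

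*Patients without the symptom at z = −1.5* (otherwise Set B): about 71% linear against 74% percentile with symptomatic patients at z = 1, so no loss; 70% against 47% with them at z = 2.

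**Step 4: how much is subtype mixing?** In Set A the large-sample efficiency of the percentile relative to the linear score is 0.86 with all symptomatic and 0.85 mixed at z = 1, and 0.58 against 0.53 at z = 2. An efficiency of 0.58 makes 35 patients worth about 35 × 0.58 = 20. Most of that loss is there before any mixing.

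**Step 5: Type I error.** With no treatment effect, the t-test rejects in 5.4% of simulated trials on the linear score and 5.3% on percentiles.

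**The case against.** The strongest reply is that the stakes are low. These are secondary outcomes of a pilot, the plan claims no power for them, and the tests remain valid. That stands, and it limits how much weight the point can carry.

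The size also rests on inputs the documents do not contain. An average of z = 2 puts the typical symptomatic patient at about the 98th percentile, while entry asks only for at least moderate severity and caps worst pain at 8. The normal reference curve is assumed too. This stands: the larger losses are conditional, and one plausible layout shows none.

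Mann-Whitney, which the plan assigns to non-normal data, softens the loss. This stands in part. It loses clearly less where the t-test loses most, but about as much in the mixed sample at z = 1 (Set A).

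The word composite in "Response will be assessed by the change in composite abdominal pain scores, bloating scores, constipation scores, and diarrhea scores" might be read as a raw scale total. That is not persuasive, because percentile is the only scoring named and the recoding is done to obtain it.

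A reader might infer that enrolling every subtype is what causes the loss. The documents do not support that. All patients must have pain, so belly pain need not divide by subtype, yet compression applies there as well. On the two bowel scales, mixing can enlarge the loss, leave it unchanged or remove it, depending on where patients without the symptom sit, which the plan does not tell us. Dilution from patients who cannot improve affects a linear score as well.

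**Conclusion.** The concern holds as a matter of precision and interpretability for aims 5, 7 and 8. The plan analyses change on a bounded, non-linear scale in patients selected for severity, so benefit is compressed in the sicker patients and the mean change depends on baseline severity.

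Under the assumptions above, t-test power at 35 per arm falls by roughly 3 to 10 points if symptomatic patients average near z = 1 (87 to 84 at the low end, 70 to 60 at the high end). Near z = 2 it falls by roughly 20 to 40 points (87 to 67, and 70 to 30). The Mann-Whitney loss is generally smaller, and in some configurations there is no loss. No single figure can be given without PROMIS baseline data.

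Two stronger readings should be resisted. The percentile does not bias the test of no difference or inflate Type I error. Nor does it touch the primary IBS-SSS endpoint or the stated sample-size calculation, neither of which uses PROMIS. This is a cheap improvement, not a defect that undermines the trial.

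**What to change.** In the PROMIS subsection, state that change from baseline to weeks 4 and 8 is analysed, for all four scales, on the standardised score derived from the same items, and that percentiles are reported descriptively only. The documents do not show whether a conversion to a standardised score is available to the team. If it is not, name the summed 0–4 item score instead. Visits, items and tests can stay as planned.

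The cost is one sentence and no new data. These scores are less familiar to readers than percentiles, which can still be tabulated. A summed score still has floor and ceiling limits and was not simulated here, so the power figures above apply to the standardised score.
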